For all studies, plasma concentrations of parent drug were low and sporadic because of the rapid and extensive hepatic metabolism of SD-809 to the active metabolites *d*₆-α-HTBZ and *d*₆-β-HTBZ. Peak plasma concentrations of the active moieties *d*₆-α-HTBZ and *d*₆-β-HTBZ were reached within 1 to 1½ hours post-dosing following administration of an immediate release formulation. Peak plasma concentrations were significantly later (median *t*_{max} 3 to 4 hours) and lower for the ER formulation without a comparable loss of exposure. In all studies where tetrabenazine was included as a control arm, deuteration was shown to significantly prolong the half-lives of both α - and β-HTBZ, resulting in an increase in exposure (~130% increase) for both active metabolites at comparable doses. Based on the pharmacokinetics over a dose range of 7.5-22.5 mg SD-809 ER, it is estimated that a 6 mg dose of SD-809 will provide an exposure (AUC_(inf)) comparable to 12.5 mg of tetrabenazine. Inhibition of CYP2D6 metabolism by paroxetine administration led to a 3-fold increase in bioavailability of *d*₆-(α+β)-HTBZ, comparatively less than has been reported with in a similar drug interaction study with tetrabenazine.

To date, five Phase 1 studies in healthy volunteers have been conducted with SD-809, including two with an immediate release formulation (powder in capsule) (AUS-SD-809-CTP-06, SD-809-C-12) and three with extended release formulations (AUS-SD-809-CTP-07 Part 1 and Part 2 and

SD-809-C-08, SD-809-C-11). In total, 100 subjects have received single doses of SD-809 or SD-809 ER, ranging from 7.5 to 22.5 mg and 24 subjects have received repeated doses of SD-809 ER for up to 5 days at 22.5 mg BID. In these studies, no SAEs were reported and all AEs were mild to moderate in intensity. Commonly reported AEs included headache, somnolence, nausea, dizziness and vessel puncture reaction. When tetrabenazine was used as a comparator, the adverse events of SD-809 were qualitatively similar to tetrabenazine. The adverse events reported with SD-809 were also consistent with prior clinical experience with tetrabenazine.

Additional information on the study results may be found in the SD-809 ER Investigator's Brochure.

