 - Individual doses of 15 to 24 mg will be given as two tablets
 - Individual doses of 27 to 36 mg will be given as three tablets

- Dose adjustments are limited to 6 mg/day (each week) (6 mg/day or 12 mg/day after a total daily dose of 48 mg is reached). Dose reductions in increments greater than 6 mg should be reviewed with the Clinical Monitor. (See Section 5.2.5)
- If a strong CYP2D6 inhibitor is started (i.e., paroxetine, fluoxetine, bupropion), the Clinical Monitor should be notified as a dose reduction of more than 6 mg may be required.

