5.2.5 Dose Reduction or Suspension

If a subject experiences a “clinically significant” adverse event (defined below)¹ that is attributed to SD-809 ER, the investigator will use his or her judgment to determine if a dose reduction or suspension is necessary. Dose adjustments should be made based on all available information including the subject’s and caregiver’s reports of adverse events and chorea control, the clinical assessment of safety and efficacy by the investigator and information from rating scales.

Dose reductions should generally occur in increments of 6 mg/day, except in the case of addition of a strong CYP2D6 inhibitor (i.e., paroxetine, fluoxetine, bupropion) or if the most recent dose increase was 12 mg/day, in which a greater dose reduction may be required. Dose reductions in this context should be reviewed with the Clinical Monitor. A dose reduction of 6 mg/day can be made by requesting that the next lowest dose level be shipped directly to the subject. Dose reductions greater than 6 mg/day should be reviewed with the Clinical Monitor. If a subject requires a dose reduction based on a telephone contact during the maintenance period, an unscheduled clinic visit should be conducted in a timely manner thereafter.

Suspension of study medication for up to one week, if warranted, is allowed.

Suspensions of study medication for adverse events must be reviewed with the Clinical Monitor before therapy is restarted. If study medication is restarted after a suspension for an adverse event, a dose reduction of 6 mg or more is permitted.

Suspensions for more than 7 days must be reviewed by the Clinical Monitor. If the subject restarts study medication within 7 days of suspension, the full dose of SD-809 ER may be resumed without titration. If subject restarts study medication greater than 7 days following a suspension, re-titration will be required.

The reason for a dose reduction or suspension must be clearly documented.

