Appendix 10: Swallowing Disturbance Questionnaire (SDQ)

Appendix 11: Strong CYP2D6 Inhibitors

Subject's receiving any of these strong CYP2D6 inhibitors will have a maximal dose of SD-809 ER of 42 mg per day.

- Bupropion
- Fluoxetine
- Paroxetine

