Subjects receiving a strong CYP2D6 inhibitor or who are poor CYP2D6 metabolizers are considered to have impaired CYP2D6 function. The following AE analyses will be repeated by impaired CYP2D6 function category at baseline (subjects receiving a strong CYP2D6 inhibitor at Baseline, subjects not receiving a strong CYP2D6 inhibitor at Baseline, CYP2D6 poor metabolizers, non-CYP2D6 poor metabolizers, subjects with impaired CYP2D6 function, and subjects without impaired CYP2D6 function):

- Overview of TEAEs
- TEAEs by SOC and preferred term

For TEAE summaries, if a subject has more than one TEAE within a preferred term, the subject is counted once in that preferred term at the maximum severity and at the closest relationship to study drug. If a subject has more than one TEAE within a system organ class, the subject is similarly counted once in that system organ class.

Complete listings of all AEs will be provided. In addition, data listings of all SAEs, AEs leading to withdrawal from the study, and AEs leading to death will also be provided.

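### SAP 9.9.1 fixes CYP2D6-inhibitor status at Baseline, so the stable-dose and entire-treatment tables count events after a later inhibitor start as uninhibited

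*SAP*

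**What the plan says.** SAP 9.9.1 defines impaired function without a time element: "Subjects receiving a strong CYP2D6 inhibitor or who are poor CYP2D6 metabolizers are considered to have impaired CYP2D6 function". The sentence that governs the tables does fix the time: "The following AE analyses will be repeated by impaired CYP2D6 function category at baseline". The inhibitor strata repeat it, one of them being "subjects not receiving a strong CYP2D6 inhibitor at Baseline". The classification is used for the overview of treatment-emergent adverse events (TEAEs) and for "TEAEs by SOC and preferred term".

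The protocol allows strong inhibitors with study drug. Appendix 11 says that subjects "receiving any of these strong CYP2D6 inhibitors will have a maximal dose of SD-809 ER of 42 mg per day". Section 5.2.1 covers a start on study: "If a strong CYP2D6 inhibitor is started (i.e., paroxetine, fluoxetine, bupropion), the Clinical Monitor should be notified". Section 5.2.5 limits the size of dose reductions "except in the case of addition of a strong CYP2D6 inhibitor", among other exceptions. Section 6.9.1 does not prohibit the three listed drugs, and its antidepressant stability rule covers only the weeks before Screening.

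Treatment continues until US commercial availability (Protocol 3). SAP Table 3 runs to Week 171, target day 1197.

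**The concern.** A label set once at Baseline is carried over a status that the protocol expects may change. Take a subject who is not a poor metabolizer and starts paroxetine at Week 20. Events after that date are tabulated with subjects who take no inhibitor and whose metabolism is intact. The reverse error occurs when an inhibitor is stopped.

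These are the only planned adverse-event tables by CYP2D6 function. The exposure-adjusted rates in SAP 9.9.1 are split by cohort and study, not by CYP2D6 status. Protocol 3.2 gives evaluation of phenotype against safety as the reason for genotyping, and Protocol 1.4 reports: "Inhibition of CYP2D6 metabolism by paroxetine administration led to a 3-fold increase in bioavailability of" the active metabolites. A subject who adds an inhibitor to an established dose is the case for which 5.2.1 and 5.2.5 make special provision, yet no planned table isolates that subject's later events.

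**Working it through.** **No figure to reproduce.** The plan states no power, event count or expected number of late starters. The check is a reading of the text plus an illustration.

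**Where the label can be wrong.**
- Duration: 171 × 7 = 1197 days, and 1197 / 365.25 = 3.28 years.
- Periods: SAP 9.9.1 performs all TEAE analyses by period. In the Week 4 and Week 8 periods the label is close in time to the events. A Week 20 starter is classified correctly there and wrongly from Week 20 on in the stable-dose and entire-treatment tables.
- Strata: of the six categories, the two based on genotype cannot change. A poor metabolizer who starts an inhibitor stays in the combined impaired stratum.

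**Illustration.** N = 116 is from Protocol 3. Everything else is assumed:
- share impaired at Baseline, b = 15% or 25%;
- share of all subjects who start an inhibitor later, s = 5%, 10% or 20%;
- event risk without and with inhibition, p0 and p1, 10% and 20% or 20% and 40% (true ratio 2.00);
- late starters spend half their follow-up inhibited, with risk pL = 1 − (1 − p0/2)(1 − p1/2).

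The risk seen in the unimpaired stratum is [(1 − b − s)·p0 + s·pL] / (1 − b). The expected number of first events under inhibition placed in that stratum is N·s·(1 − p0/2)·p1/2.

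Example with b = 25%, s = 20%, p0 = 10%, p1 = 20%: pL = 1 − 0.95 × 0.90 = 0.145. Observed risk = (0.55 × 0.10 + 0.20 × 0.145) / 0.75 = 0.112. Ratio = 0.20 / 0.112 = 1.79. Misplaced events = 116 × 0.20 × 0.95 × 0.10 = 2.2.

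| b | s | Ratio seen (misplaced events), 10% vs 20% | Ratio seen (misplaced events), 20% vs 40% |
|---|---|---|---|
| 15% | 5% | 1.95 (0.6) | 1.95 (1.0) |
| 15% | 10% | 1.90 (1.1) | 1.91 (2.1) |
| 15% | 20% | 1.81 (2.2) | 1.83 (4.2) |
| 25% | 5% | 1.94 (0.6) | 1.95 (1.0) |
| 25% | 10% | 1.89 (1.1) | 1.90 (2.1) |
| 25% | 20% | 1.79 (2.2) | 1.81 (4.2) |

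The illustration pools the cohorts, ignores subjects who stop an inhibitor, and gives late starters the common risk before they start.

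**The case against.** A Baseline subgroup is conventional and avoids conditioning on treatment changes that events may themselves cause. That stands, and it is a reason to keep these tables.

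The effect is also small against the noise. Take assumed risks of 50% and 30% with 15% to 25% of 116 impaired. The standard error of the difference is √(0.25/17.4 + 0.21/98.6) = 12.8 points or √(0.25/29 + 0.21/87) = 10.5 points. It would be larger within cohorts, which SAP 8.7 makes the default. The study is descriptive (SAP 8.1). This limits the importance of the point but does not correct the classification.

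A reader might infer a larger attenuation by giving each late starter the full inhibited risk. The observed difference is then (1 − f) times the true one, where f is the share of Baseline non-users who start. A 20-point difference becomes 18, 16 or 14 points at f = 10%, 20% or 30%. This treats starters as inhibited for the whole event window, so it is an upper-end case on assumed inputs.

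SAP 9.4 summarizes concomitant medications both during treatment and at baseline, so comparing the rows for each drug would hint at the number of starters. It would not link events to inhibited time. Protocol 6.13 allows withdrawal for interfering medication, but this is optional, and 5.2.1 and 5.2.5 manage such subjects on study.

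An on/off analysis has its own bias. Depression that prompts the drug is assigned to off-inhibitor time, and with first-event rates that subject then adds no on-inhibitor time for depression. This also stands, and it argues for a supplement rather than a replacement.

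**Conclusion.** The point holds for the stable-dose and entire-treatment tables, for subjects who are not poor metabolizers and start a strong inhibitor after Baseline, and in reverse for those who stop one. Under the assumptions above, a true ratio of 2.00 would appear as 1.95 to 1.79, with about 0.6 to 4.2 first events misplaced. The real share of late starters is unknown and could be small.

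A reader might go further and infer that all the CYP2D6 tables are wrong, or that the plan would make the interaction look harmless. The documents do not support either. Early-period and genotype tables are little affected or unaffected. The 3-fold figure concerns bioavailability, not event risk. Dose is individualized, capped under inhibition and may be reduced when an inhibitor is added, so no classification gives an equal-dose comparison. Attenuation is not assured for depression, since the event may lead to the prescription. This is a cheap improvement to a descriptive analysis, not a flaw that invalidates it.

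**What to change.** Keep the Baseline-category tables and add to SAP 9.9.1:
- exposure-adjusted first-event rates for the TEAE overview categories and the AEs of interest, with events and person-time split by strong-inhibitor status at onset, derived from concomitant-medication start and stop dates, and with poor-metabolizer status held fixed;
- the number and a listing of subjects who start or stop a strong inhibitor on study.

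No new data are needed. Protocol 6.9.1 records dates of administration, and SAP 9.9.1 already defines first-event person-time. The cost is SAP wording and programming.

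State the downsides with the analysis. SAP 9.4 covers missing start dates, but partial dates need a rule. On-inhibitor person-time is likely to be small. That time comes later in follow-up, while off-inhibitor time includes titration, and it excludes subjects who already had the event. Depression rates in particular need cautious reading.

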The U.S. prescribing information for tetrabenazine indicates that CYP2D6 genotyping should be performed at dose levels higher than 50 mg, although genotyping is often not performed in clinical practice as the drug is titrated. In the present study, CYP2D6 genotyping will be performed in a blinded manner to allow evaluation of the effect of phenotype on safety parameters at the conclusion of the study.

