5 STUDY TREATMENT

The study medication to be used in this trial is an extended release (ER) formulation of SD-809. Three dose strengths of SD-809 ER will be available for use: 6, 9, and 12 mg tablets. Each dose strength will have a black marking of SD 6, SD 9 or SD 12, corresponding to the dose strength and a distinct tablet color: 6 mg - purple; 9 mg - blue; 12 mg - beige.

5.1 *Investigational Product*

The investigational product is a matrix formulation and is designed as a gastro-erosional, extended release tablet to be administered with food. Study drug is coated with a colored polymer coating to aid in swallowing. The colored polymer coating is applied to the tablets according to dose strength; 6 mg - purple; 9 mg - blue; 12 mg - beige. Each dose strength will have a black marking of SD 6, SD 9 or SD 12, corresponding to the dose strength. SD-809 ER tablets have been manufactured according to current Good Manufacturing Practices regulations. During titration/dose adjustment, SD-809 ER tablets will be supplied in weekly blister packs as 6, 9, and/or 12 mg tablets and will be labeled according to applicable regulatory guidelines. Each blister pack will contain a sufficient supply of drug until the next specified visit, plus overage to account for potential delays in study visits or evaluations or receipt of their supplies. **Once the investigator determines that a stable dose has been reached, SD-809 ER will be supplied in 30 count containers and labeled according to applicable regulatory guidelines.**

Complete details regarding SD-809 ER supply, dispensing and ordering will be provided in the study Operations Manual.

SD-809 ER tablets must be stored in a secure area with access limited to authorized staff, protected from light at controlled room temperature, 15°C to 25°C (59°F to 77°F).

5.2 *Treatment Regimen*

5.2.1 *General Guidelines*

The following general guidance applies to treatment regimens for all subjects in the study:

- All treatment regimens will be administered with meals
- A daily dose of 6 mg will be given once a day in the morning and daily doses of 12 mg and higher will be administered twice daily, approximately 10 hours apart during the day.
- The maximum total daily dose of SD-809 ER is 72 mg (36 mg BID), unless the subject is receiving a strong CYP2D6 inhibitor (See Appendix 11), in which case the maximum total daily dose is 42 mg
 - Individual doses up to and including 12 mg are given as a single tablet

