8.3 Safety Analyses

Safety and tolerability will be assessed throughout the study by monitoring the following parameters:

 • Adverse events (AEs) • Clinical laboratory tests • Physical examination • Vital signs • 12- lead ECGs • Epworth Sleepiness Scale (ESS) 	
 • Columbia Suicide Severity Rating Scale (C-SSRS) • Unified Huntington’s Disease Rating Scale (UHDRS) • Swallowing Disturbance Questionnaire (SDQ) • Unified Parkinson’s Disease Rating Scale (UPDRS), dysarthria item • Barnes Akathisia Rating Scale (BARS) • Hospital Anxiety and Depression Scale (HADS) • Montreal Cognitive Assessment (MoCA©)
---	--

Safety data will be summarized descriptively for the overall population and based on prior treatment [SD-809 ER or placebo (Rollover subjects) or tetrabenazine (Switch subjects)]. Descriptive statistics will be calculated for quantitative data and frequency counts and percentages will be provided for categorical data. Descriptive statistics of change-from-baseline for Rollover subjects will utilize the Baseline from Study SD-809-C-15 (C-15 Baseline) and the Baseline from the present study (C-16 Baseline), as appropriate, and will be specified in the Statistical Analysis Plan.

The nature, frequency, and severity of adverse events will be tabulated for all subjects combined and by treatment. Baseline, within study, end of study, and change-from-baseline values for clinical laboratory evaluations and vital signs will be summarized as appropriate.

Treatment-emergent adverse events and laboratory, vital sign, and ECG parameters will be summarized. In addition, change from baseline will be summarized for laboratory and vital sign parameters. Shift tables will be provided for clinical laboratory results. ECG results will be classified as normal and abnormal and summarized.

8.4 *Safety Endpoints*

The following safety endpoints will be assessed:

- Incidence of adverse events (AEs), serious AEs, severe AEs, drug related AEs, AEs leading to withdrawal during the following periods:
 - Overall
 - During titration in Rollover subjects (up to 8 weeks)
 - During dose adjustment in Switch subjects (up to 4 weeks)
 - During long term treatment
- Observed values and changes from baseline in clinical laboratory parameters (hematology, chemistry, and urinalysis)
- Observed values and changes from baseline in vital signs
- Observed values in ECG parameters and abnormal findings

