- Number of subjects with on-treatment QTcF values > 450ms, > 480ms, > 500ms
- Observed values and changes in UHDRS, UPDRS (dysarthria), BARS, HADS, ESS, C-SSRS, and MoCA©
- Duration of time to achieve stable doing of SD-809 ER

8.5 *Sample Size*

Because this is an open label safety study, the sample size is not based on statistical considerations.

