9.9.5 Electrocardiogram (ECG)

A safety electrocardiogram (ECG) will be recorded at Screening and the Week 8 visit for all subjects. For subjects on allowed doses of citalopram or escitalopram, additional ECGs will be performed at Week 1 (Switch subjects) or Week 2 (Rollover subjects) and at Week 4 if the dose of study drug has been increased since the last ECG.

A cardiologist will provide a clinical interpretation of each ECG that will be recorded in the eCRF. ECG parameters that will be recorded include heart rate, PR interval, QRS duration, QT interval, and QTcF (QT interval corrected for heart rate using Fridericia's formula).

Descriptive statistics will be used to summarize ECG parameters at Screening and the Week 8 visit. Descriptive statistics will also be used to summarize QTcF values at Screening and the Week 8 visit for subjects with a QTcF value >450 msec at any visit. These analyses will be repeated for the Screening, Week 1 (Switch subjects) or Week 2 (Rollover subjects), Week 4, and Week 8 visits for subjects receiving allowed doses of citalopram or escitalopram at Baseline.

The number and percentage of subjects with normal, abnormal not clinically significant, abnormal clinically significant, and abnormal with clinical significance not specified ECGs will be summarized at Screening and the Week 8 visit. The number and percentage of subjects with PR >200 msec, QRS >100 msec, QT >500 msec, QTcF >450 msec, QTcF >480 msec, and QTcF >500 msec, will be similarly summarized. These analyses will be repeated for the Screening, Week 1 (Switch subjects) or Week 2 (Rollover subjects), Week 4, and Week 8 visits for subjects receiving allowed doses of citalopram or escitalopram at Baseline.

ECG results will also be listed.

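### CYP2D6 genotyping was meant to inform safety parameters in general, but the SAP examines CYP2D6 function for adverse events only and leaves QTcF without that split

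*SAP*

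**What the plan says.** **Purpose of genotyping.** Protocol 3.2 has CYP2D6 genotype determined blind "to allow evaluation of the effect of phenotype on safety parameters at the conclusion of the study". It does not limit this to adverse events.

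**Safety parameters.** Protocol 8.3 opens its list with "Safety and tolerability will be assessed throughout the study by monitoring the following parameters", and the list includes 12-lead ECGs. Protocol 8.4 adds the endpoint "Number of subjects with on-treatment QTcF values > 450ms, > 480ms, > 500ms".

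**CYP2D6 in the SAP.** SAP 9.9.1 defines the group: "Subjects receiving a strong CYP2D6 inhibitor or who are poor CYP2D6 metabolizers are considered to have impaired CYP2D6 function". It then says "The following AE analyses will be repeated by impaired CYP2D6 function category at baseline" and names two outputs: the overview of treatment-emergent adverse events (TEAEs), and TEAEs by system organ class and preferred term. Otherwise, poor-metabolizer status appears among the baseline characteristics (SAP 9.2), and the genotype in the assessment schedules and laboratory list.

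**ECG in the SAP.** SAP 9.9.5 summarizes ECG parameters and threshold counts at Screening and Week 8. It repeats them only "for subjects receiving allowed doses of citalopram or escitalopram at Baseline". It also summarizes QTcF at those two visits for subjects with any value above 450 ms.

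**Dose limits.** Protocol 5.2.1 states: "The maximum total daily dose of SD-809 ER is 72 mg (36 mg BID), unless the subject is receiving a strong CYP2D6 inhibitor", in which case the limit is 42 mg. No limit depends on genotype.

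**The concern.** The protocol collects genotype to see whether metabolizer status affects safety, and it makes QTcF a named safety endpoint. The SAP never brings the two together. It builds the CYP2D6 subgroups for adverse events, and it builds an ECG subgroup for two antidepressants, but it has no ECG table by CYP2D6 function.

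The planned ECG tables are by cohort. If QTcF exceedances were concentrated in poor metabolizers, those tables would look the same as if the exceedances were spread evenly. The final report would then have no planned tabulation on part of the question for which subjects were genotyped. The cohort tables remain valid for what they show.

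**Working it through.** No power, alpha or sample-size figure is involved. The check is a comparison of texts plus some illustrative arithmetic.

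1. **Coverage.** Protocol 8.3 lists 6 parameters in one column (adverse events, laboratory tests, physical examination, vital signs, ECG, ESS) and 7 in the other (C-SSRS, UHDRS, SDQ, UPDRS dysarthria, BARS, HADS, MoCA): 6 + 7 = 13. The SAP has a CYP2D6 split for 1 of them, adverse events, in two outputs. The other 12, ECG included, have none.

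2. **Do the split adverse event tables already carry QTcF?** Only in part. Protocol 7.1.1 gives an abnormal ECG as an example of an adverse event when it is clinically significant and leads to treatment or a diagnosis. It gives any abnormal safety assessment as an example when it leads to a dose change, discontinuation or treatment. A QTcF value above 450 or 480 ms with no such consequence need not be recorded as an adverse event.

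3. **Permitted doses.** Steps are 6 mg/day each week, and 6 or 12 mg/day once 48 mg is reached.
   - Rollover: 6, 12, 18, 24, 30, 36, 42, 48 mg, with 48 mg reached at Week 7. The Week 8 ECG is therefore taken at 48 mg at most.
   - Switch starting at 24 mg: 30, 36, 42, 48, 60, 72 mg, with 72 mg reached at Week 6.
   - Uncapped against capped maximum: 72/42 = 1.71.

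4. **Exposure in poor metabolizers (extrapolated).** Protocol Appendix 15 gives SD-809 AUC of 1740 at 18 mg and 2435 at 24 mg. Tetrabenazine 50 mg, the daily limit for known impaired function, gives 4200 to 4228. Two assumptions are used above 24 mg: proportionality, 2435 × dose/24; and the local slope, (2435 − 1740)/6 = 115.8 per mg.

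| SD-809 dose | Proportional | Local slope | Ratio to tetrabenazine 50 mg |
|---|---|---|---|
| 42 mg | 4261 | 4520 | 1.01–1.08 |
| 48 mg | 4870 | 5215 | 1.15–1.24 |
| 72 mg | 7305 | 7995 | 1.73–1.90 |

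   Appendix 15 stops at 24 mg of SD-809, and its ranges are wide (1451 to 4723 around 2435).

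5. **What a cohort table can hide (assumed counts).** Take the planned 80 Rollover subjects, 6 of them poor metabolizers, and 4 subjects above 450 ms: 4/80 = 5.0%. The same row fits 0/6 against 4/74 (5.4%), and 3/6 (50%) against 1/74 (1.4%). At Week 8 these subjects can be at no more than 48 mg, so the 72 mg line above does not belong with this example.

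6. **Size of the subgroup.** The documents do not give the number of poor metabolizers. If 5% to 10% is assumed, 116 × 0.05 = 5.8 and 116 × 0.10 = 11.6, or about 6 to 12 subjects. With no exceedances in 6, the one-sided 95% upper limit is 1 − 0.05^(1/6) = 39%; in 12 it is 1 − 0.05^(1/12) = 22%.

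7. **Timing of ECGs.** Both schedules of events include an ECG at End of Treatment or early termination. SAP 9.9.5 tabulates Screening and Week 8 for all subjects. Under SAP 8.9, an End of Treatment ECG can stand in for Week 8 only if it falls on days 53 to 80 and there is no scheduled Week 8 record. A CYP2D6 split of the existing tables would therefore miss Rollover doses above 48 mg, which are possible only after the Week 8 ECG.

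**The case against.** The strongest reply is that nothing specified was dropped. Protocol 3.2 is a design rationale; it says genotyping allows an evaluation, not that every parameter will be tabulated by phenotype. Protocol 8.3, 8.4 and 8.6 set no CYP2D6 safety subgroup, so the two TEAE outputs over six categories go beyond Protocol section 8. This stands. A reader might infer that the SAP breaches the protocol, or that SAP 8.10 had to record the restriction. The documents do not support that, because 8.10 covers changes to protocol-specified analyses and this was not one.

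Second, the information is retrievable. Poor-metabolizer status, ECG results and dose changes are listed, SAP 8.4 allows exploratory analyses, and ECG findings that altered care enter the split TEAE tables. This stands in part: it leaves hand matching or a post-hoc table. The population pharmacokinetic analysis explores covariates of exposure, not of QTcF.

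Third, the risk is easily overstated. A reader might take the ratios of 1.73 to 1.90, or the masking example, as a sign of QT danger. The documents contain no exposure–QTcF relationship, the doses are permitted rather than expected (upward titration stops once chorea is controlled), and the counts are invented. Protocol 1.4 reports that "Inhibition of CYP2D6 metabolism by paroxetine administration led to a 3-fold increase in bioavailability" of the active metabolites, but applying that to poor metabolizers is an inference. The same section says deuteration reduces the impact of genotype compared with tetrabenazine. Entry criteria also exclude prolonged QTcF and most QT-prolonging drugs. All of this stands.

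**Conclusion.** The point holds as a narrowing of a stated purpose. CYP2D6 function is examined for 1 of 13 safety parameters, and the QTcF endpoint is left out although the subgroups are already defined and the data already collected. QTcF is the omission worth repairing for two reasons that rest on the text alone: poor metabolizers are the impaired group without the 42 mg cap, and isolated exceedances need not appear in the split adverse event tables.

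A reader might also infer that all 13 parameters must be split. Protocol 3.2 does not say so, and laboratory tests and rating scales can stay as they are.

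The number of poor metabolizers (6 to 12 assumed), the exceedance counts and the exposures at 42 to 72 mg are assumptions. They show why the split is useful, not that a QT problem exists. The content of SAP Appendix 1 (interim analysis) is not visible, but Protocol 3.2 places the phenotype evaluation at the end of the study, which is what this SAP covers.

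**What to change.** In SAP 9.9.5, add:

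- the QTcF summary and the counts above 450, 480 and 500 ms by the CYP2D6 categories of SAP 9.9.1, Rollover and Switch cohorts combined;
- poor metabolizers shown separately from strong-inhibitor users, because only the latter are capped at 42 mg;
- the End of Treatment or early termination ECG alongside Screening and Week 8, so that exposure after Week 8 is covered;
- if poor metabolizers are few, a listing of each one's QTcF with the daily dose at that ECG.

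The cost is a few further tables from data already collected, with subgroups already programmed for the TEAE outputs. The drawback is small groups: even no exceedances in 6 to 12 subjects would leave upper limits of 39% to 22%, so the tables should be labelled descriptive. A sentence in SAP 8.10 limiting the phenotype evaluation to TEAEs would document the choice but would not answer the question for which genotype was collected.
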